7.2.4 Change of regimen for adverse events

A change of regimen for an adverse event is defined as when a patient's regimen is modified in any way (including stopping a drug, changing the dose of a drug or starting a new drug) with the reason being an adverse event.

The difference in proportion of patients who have a change of regimen for adverse events between Regimen B and Regimen C, between Regimen B_{mox} and Regimen C, between Regimen B and Regimen D, will be calculated.

The MedDRA SOC/SMQ or preferred term of the adverse event and the type of treatment change, will be described by arm.

7.2.5 Pharmacokinetics/Pharmacodynamics

At a number of visits throughout the trial, a single blood sample is taken to determine the bedaquiline (BDQ) and M2 plasma concentrations. The BDQ plasma concentrations are used by a qualified vendor to estimate C_{trough} , C_{max} and AUC using empirical Bayes' estimation based on a population pharmacokinetic model. Individual ART plasma concentrations (LPV, RTV and NVP) and 4β -hydroxycholesterol/cholesterol ratio (as a measure of cytochrome P450 3A (CYP3A) activity) are also measured.

Participants randomised to Regimen C or Regimen D with PK data available, will be classified into 5 subgroups based on their HIV status and HIV drugs taken immediately before the PK blood draw:

- **HIV Neg:** HIV negative at baseline
- **HIV Pos, LPV/r**: HIV positive at baseline having received Liponavir/Ritonavir (but not Nevirapine) immediately before the PK blood draw.
- HIV Pos, NVP: HIV positive at baseline having received Nevirapine (but not Liponavir/Ritonavir) immediately before the PK blood draw.
- **HIV Pos, other ARV**: HIV positive at baseline having received ART (but not Liponavir/Ritonavir or Nevirapine) immediately before the PK blood draw.
- **HIV Pos, not taking ARV:** HIV positive at baseline but not receiving ART immediately before the PK blood draw.

Individual plasma concentrations will be listed and descriptive statistics generated at each sampling time, by treatment group and separately for the above defined subgroups.

Further details of the analyses of PK/PD will be described in the STREAM Stage 2 Extensive SAP.

7.3 **Health Economics**

In selected sites, acceptability of Regimens A, B, C and D to stakeholders will be analysed in terms of:

- Costs to the health system
- Household costs
- Patient treatment and support experiences
- Health worker experiences.

The analyses of health and household costs and patient and health worker experiences will be described in a separate document.

7.4 **Testing multiple outcomes**

We will make no adjustment to p-values or confidence intervals to allow for testing multiple secondary outcomes.

The STREAM primary outcome is a composite outcome of bacteriological failure, treatment failure for any reason (clinical, bacteriological, intolerance) and death. The primary analysis is non-inferiority of Regimen C versus Regimen B. If the 95% CI for the treatment effect

(difference in proportion unfavourable by 76 weeks (C-B)) lies below the non-inferiority margin, then we will also test for superiority; because this is a closed test procedure there is no issue of multiplicity.

Secondary outcomes are divided in the protocol into efficacy outcomes, safety outcomes and acceptability outcomes. For safety outcomes it is appropriate to test each independently since it is important to identify any risks associated with Regimen C. The secondary efficacy outcomes are mostly components of the primary outcome or very closely related to the primary outcome (bacteriological and clinical outcomes). We will not adjust for multiple testing for these since they are correlated with the primary outcome (so standard adjustments are conservative).

We will report significance tests for differences between treatment arms for acceptability outcomes, but if we have failed to demonstrate non-inferiority of Regimen C versus Regimen B for the primary outcome, we will not use significance tests for these acceptability outcomes to conclude superiority.

8 ADDITIONAL EXPLORATORY ANALYSES

The following analyses will all be completed after the last participant has reached Week 132 on the mITT population unless otherwise stated.

8.1 Time to cessation of clinical symptoms based on PI assessment

In stage 2 of STREAM, the presence of a productive cough, fever, and night sweats was only solicited at the randomisation visit. During follow-up these symptoms were recorded on the AE log if reported by the participant. There is concern that these events have been under reported. Therefore, the proportion of people reporting these symptoms in Regimen B will be compared to the proportion reported in stage 1 (when they were solicited at each visit). If this proportion is <80% of that seen in stage 1, the following analyses will not be conducted.

Time to cessation of clinical symptoms is defined as the time from randomisation to the first of two consecutive visits where cessation of **all three** of the TB symptoms: a productive cough, fever, and night sweats, as reported by the patient. Patients with none of the TB symptoms at screening and baseline with be excluded from this analysis. This definition matches the definition of time to culture conversion as the first of two consecutive symptom-free months. For patients who do not cease clinical symptoms, cessation of clinical symptoms will be censored at the patients' last visit up to and including week 76.

Median time to cessation of clinical symptoms will be calculated for Regimen B, Regimen C, and Regimen D.

A hazard ratio with corresponding two-sided 95% confidence intervals and p-value will be estimated for the comparison of Regimen B with Regimen C, and Regimen B with Regimen D. A Cox Proportional Hazards model will be used, adjusted for randomisation protocol (as defined in Section 1.6) and the stratification factor HIV status with the three categories of: HIV negative; HIV positive with CD4 count ≥350 cells/mm³; and HIV positive with CD4 count <350 cells/mm³.

The equality of survivor functions for time to cessation of clinical symptoms for Regimen B and Regimen D, will each be compared using a (Wilcoxon)

Log rank test, stratified by randomisation protocol (as defined in Section 1.6) and the randomisation stratification factor HIV status with the three categories of: HIV negative; HIV positive with CD4 count ≥350 cells/mm³; and HIV positive with CD4 count <350 cells/mm³.

The assumption of proportional hazards between the two comparisons will be tested using the proportional hazards test based on the Schoenfeld residuals after fitting the Cox Proportional Hazards models. In the case where there is adequate evidence that the proportional hazard assumptions are violated at the 5% level (i.e. p<0.05), methods where proportional hazards is not a necessary assumption will be used, such as restricted mean survival time.

8.2 WHO classification of outcome

TB outcome at the end of treatment will be determined using the WHO DR-TB treatment outcomes definition¹¹. Participants will be classified as cured, treatment completed, treatment failed, died, lost to follow-up or not evaluated, with the first two categories considered together as treatment success.

The modified WHO DR-TB treatment outcome definition will also be applied; this includes an additional category of relapse after treatment success, defined as bacteriological relapse after end of treatment cure^{4,12}.

The most recent WHO DR-TB treatment outcome definition¹³ will also be applied; this moves away from bacteriological status and focuses more on the completion of treatment or reasons for incompletion.

Each classification will be tabulated by treatment arm and the unadjusted difference in treatment success comparing Regimen B with Regimen C, Regimen B with Regimen D and Regimen C with Regimen D calculated with 95% confidence intervals.

8.3 **TB outcome irrespective of treatment changes at Week 132**

This analysis will exclude all participants whose scheduled last efficacy visit is before Week 132.

TB outcome will be classified according to the patients' culture status at week 132 regardless of treatment changes or intermediate culture results – similar to a simplistic intention-to-treat analysis.

A participant is defined as "cured at Week 132" if the last two cultures were negative with the last no earlier than the Week 132 analysis window; other categories include death prior to Week 132, last culture positive at Week 132, last culture negative prior to Week 132, last culture positive prior to Week 132, or no cultures after baseline.

This classification will be tabulated by treatment arm, and the difference in proportion cured reported comparing Regimen B with Regimen C, Regimen B with Regimen D and Regimen C with Regimen D calculated with 95% confidence intervals, stratifying for randomisation protocol and HIV status.

8.4 Lung surgery

The proportion of participants having undergone lung surgery (resection or pneumonectomy) by Week 76 and Week 132 in Regimen C and Regimen D will be compared to Regimen B using Fisher's exact test on the safety population.

9 DATA SUMMARIES

9.1 Recruitment and baseline characteristics

9.1.1 Recruitment, screening, & eligibility

The number of patients screened, randomised, and treated will be tabulated by centre and treatment arm. The number of patients who failed screening, and the reasons for ineligibility will be presented by randomised group.

9.1.2 Exclusions from analysis

The number of patients excluded from the mITT and PP analysis populations will be tabulated by treatment arm and by reason for exclusion.

9.1.3 Baseline characteristics

All eligible patients randomised will be included in tables of baseline comparisons by treatment group. Characteristics will include sex, age, race, height, weight, BMI, albumin levels, and laboratory parameters such as, HIV status, CD4 count (if applicable), smear and culture status, and drug susceptibility status for a number of TB drug types. The baseline characteristics table will be repeated for each of the ITT, safety, PP and mITT populations.

9.2 Efficacy and adherence

Each analysis will be carried out using the mITT analysis population.

9.2.1 Sputum smear and culture

Sputum smear and culture results (positive or negative) will be tabulated by visit and treatment arm.

9.2.2 Adherence

Adherence will be summarised by treatment arm as the percentage of each of the intensive and continuation phase doses completed and overall across both phases.

9.2.3 Drug resistance

All drug resistance analyses will be based on phenotypic DST results unless unavailable when genotypic results will be used.

Drug resistance at screening or baseline will be tabulated by treatment arm.

Acquired resistance to any drugs will also be described and tabulated by treatment arm using i) the last available DST result for each drug for each patient, and ii) all available post-randomisation DST result (i.e. classifying as resistant if any result is resistant) for each drug for each patient ignoring isolated resistance unless it is the last result prior to the point of analysis. The proportion of participants developing resistance, especially resistance leading to the development of pre-XDR or XDR strains of TB in Regimen C and Regimen D will be compared to that in Regimen B for data up to Week 76, and for the Allocated treatment phase only (i.e. up to the point of starting a salvage regimen).

9.3 **Safety**

All the following analyses will be on the safety population.

9.3.2 Liver function

Bilirubin, ALT, and AST will be tabulated by DAIDS grade, visit and treatment arm. Mean (and SE) bilirubin, ALT, and AST will be presented by visit and treatment arm. The number of patients experiencing more than or equal to five times above the upper normal limit will be tabulated by arm.

9.3.3 Hearing impairment

The proportion of patients experiencing significant hearing loss (unilateral or bilateral) based on Brock's Criterion applied to Shoebox data, during treatment and follow-up will be tabulated by treatment arm. Significant hearing loss will be defined as hearing loss that persists such that it is still present at the last visit of the follow-up period being considered (Week 76 or last efficacy visit) and is grade 3 or higher.

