#### 1.1.6 Duration of follow-up

All patients in Stage 1 of the study will be followed up to Week 132. The primary analysis will be based on the data accrued to Week 132.

All patients in Stage 2 of the study will also be followed up to Week 132, 56 weeks beyond the primary analysis point at Week 76. The main purpose of this extended follow-up is to monitor safety outcomes, particularly deaths. Recruitment to Stage 2 was slower than initially expected, as several sites closed to recruitment early due to their NTP adopting a fully oral regimen in line with changing WHO Guidelines. Given the urgent need for evidence to contribute to global guidelines on all-oral treatment regimens, with Version 11 of the protocol the end of follow-up for efficacy has been brought forward, although follow-up for safety is unchanged; follow-up for efficacy will end when the last patient recruited is projected to have reached Week 96. This will allow microbiology results to be

complete by the end of the trial, facilitating rapid analysis and reporting of Stage 2 results. The impact of shortening the follow up period for efficacy is minimal, and outweighed by the benefits of earlier availability of long-term trial results. The majority of patients (approximately 75% on Regimens B and C) will still have efficacy outcomes at Week 132, but for a proportion of patients (those randomised towards the end of the recruitment phase) efficacy follow-up will be censored between 96 and 132 weeks. The reduction in the total person-years of follow-up for the efficacy analysis is small, only 3% in Regimens B & C.

In summary, in Stage 2 the primary analysis will be based on the data accrued to Week 76; the data accrued to the date when the last patient is projected to have reached Week 96 will be used for the secondary long-term efficacy analysis and all data to the end of trial at Week 132 will be used for the long-term safety analyses.

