The following assessment schedule applies to all treatment arms in the STREAM trial as soon as Stage 2 begins (for sites participating in Stage 2).

Observation/Investigation	Screening	Randomisation		Treatment Phase		
				Intensive Phase		Follow-up
			Weeks 1 – 3	Weeks 4 onwards		
Written informed consent	Х	X				
Demographics	Х	X				
Medical History	X	X				
Alcohol Use Questionnaire		X		Week 16	Week 32	Week 52
Clinical Examination	Х	X	X	X	X	Х
Clinical assessment (including AEs and concomitant medication during treatment)	Х	х	х	Х	Х	Х
Height		Х				
Weight	Х	Х	X	Х	X	Х
Visual acuity and colour tests		Х		Week 12 (and if symptoms)	Week 28 and 40 (and if symptoms)	
Hearing test	Х		Week 1 (If clinically indicated)	Week 4, 8 and 16	At the start of the continuation phase  , Week 28 and 40	Weeks 52, 76 and 132
Haemoglobin		Х				
HIV antibody test	Х					Week 76 
CD4 (in HIV positive patients)	Х		According t	o national guidelines, a	at end of BDQ dosing an	nd at week 132
Viral load (in HIV positive patients)	Х			X 	X 	X 
Hepatitis A, B and C testing		Х				
Urinalysis (sample sent to) central lab		Х	X	X	X	X 
Urine: HCG Pregnancy test	Х	Х		If clinically indicate	ed and at end of study	
Chest X-ray 	Х					
ECG (12-Lead) 	Х	Х	X	Х	Х	Х
Additional Post-Dose ECG (12 Lead) for sites in PK study 			Week 2	Week 12	Weeks 24 & 40	
Sputum smear and culture 	X 	X 		X 	X 	X 
Sputum for drug resistance testing	X 					
Patient's costs (in selected sites)		Х		X 	X 	X 
Blood sample for storage (if consents) 		X 			X 	
PK samples 		Х	Week 2	Weeks 4 & 12	Weeks 24 & 40	Weeks 76, 120 & 132

STREAM Protocol V111 15 Dec 2020

Laboratory safety tests 	Х	Х	Х	X	X 
TSH & thyroxine of free thyroxine	X				Weeks 40 & 76

X indicates assessments required at particular visits

-  At screening and randomisation two samples will be collected, with an additional third early morning sample if possible. Two samples will be collected at each subsequent visit, ideally one early morning and one spot sample, or two spot samples if the patient does not provide an early morning sample. Refer to the STREAM Microbiology Manual for details of the tests to be undertaken.

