1.4 Study interventions

In Stage 2 of the STREAM trial, the primary comparison being made is between Regimen C and Regimen B, with secondary comparisons between Regimen D and Regimen B. In addition, a limited number of secondary analyses will make comparisons between Regimen A and the other regimens.

Regimen A: The locally-used MDR-TB regimen in accordance with 2011 WHO MDR-TB treatment guidelines¹.

Regimen B: Regimen B forms the control regimen for the primary and secondary comparisons, and is based on the regimen described by Van Deun 2010^2 (updated results³) consisting at the start of STREAM of clofazimine, ethambutol, moxifloxacin, and pyrazinamide given for 40 weeks, supplemented by isoniazid, kanamycin, and prothionamide for the first 16 weeks; this combination is referred to as Regimen B_{mox}. With Version 8.0 of the protocol Regimen B is modified by replacement of moxifloxacin with levofloxacin (referred to as Regimen B_{lev}). Regimen B without specification of which fluoroguinolone is in the regimen

refers to either (B_{mox} or B_{lev}). With Version 10.0 of the protocol, Regimen B is further modified to replace kanamycin with amikacin in sites where:

- the national TB program has replaced kanamycin with amikacin in line with revised WHO guidance⁴ and
- amikacin is available for the trial.

Kanamycin will continue to be used until the transition takes place within each country programme.

Regimen C: Regimen C is an all-oral modified version of Regimen B, consisting of bedaquiline, clofazimine, ethambutol, levofloxacin, and pyrazinamide given for 40 weeks, supplemented by isoniazid, and prothionamide for the first 16 weeks.

Regimen D: Regimen D a shortened modified version of Regimen B, consisting of bedaquiline, clofazimine, levofloxacin, and pyrazinamide given for 28 weeks, supplemented by isoniazid, and kanamycin for the first 8 weeks.

All patients in Stage 2 of the study will be followed up to Week 132. The primary analysis will be based on data accrued to Week 76; the data accrued to the date when the last patient is projected to have reached Week 96 will be used for the secondary long-term efficacy analysis; all data accrued to Week 132 will be used in the long-term safety analysis.

1.5 **Treatment phases**

Regimen B, Regimen C, and Regimen D each consist of 2 phases; an intense phase followed by a continuation phase, as shown in Figure 1.

[figure not shown]

Figure 1: Regimen treatment phases

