5.8 Adverse events

For all analyses of adverse events (AE), only treatment-emergent AEs will be included. An AE will be considered treatment-emergent in a particular phase if it is worse in severity than the corresponding baseline observation. If the baseline observation is missing, the AE is always considered as treatment-emergent. For ECG, laboratory events, weight changes and hearing loss, only the maximum grade within phase will be reported. For laboratory and weight AEs, a shift from 'abnormally low' at baseline to 'abnormally high' post baseline (or vice versa) is also treatment-emergent. Laboratory AEs starting on day 1 will be considered treatment emergent since it is impossible to know whether the blood samples were taken before or after administration of the first dose of trial treatment and this is the most conservative approach.

SAEs will be analysed as episodes, with all components of the same clinical SAE presented as one episode. Analyses of grade 3 or 4 adverse events will consider each component as separate events. Hearing loss reported in the left and right ear as two separate AEs but with overlapping start and stop dates will be reported in analyses as one AE of bilateral hearing loss at the maximum grade of the two unilateral events.

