7 ANALYSIS OF SECONDARY OUTCOMES

7.1 Efficacy outcomes

Secondary efficacy analyses will be carried out on i) data censored at Week 76, and ii) data from all visits occurring on or before the projected Week 96 visit of the last patient randomised i.e. approximately end of November 2021 (long-term efficacy data). A participant's scheduled last efficacy visit will be their latest scheduled trial visit on or before this date. In addition to the comparisons detailed below, analyses of the long-term efficacy data will include comparisons of Regimen C with Regimen D. Comparisons of Regimen C and Regimen D using data up to Week 76 were carried out at the time of the primary analysis but considered exploratory.

Secondary efficacy outcomes will be analysed on the mITT analysis population with the exception of the analysis of favourable outcome at Week 132 to determine the non-inferiority of Regimen C to Regimen B which will be analysed on the mITT, PP and mPP populations.

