This analysis will be conducted on the whole study period, and separately for follow-up censored at Week 76. It will also be repeated comparing bedaquiline and non-bedaquiline regimens (Regimens A and B vs C and D) and comparing Regimen B_{mox} and Regimen C, and Regimen B_{lev} and Regimen C. A descriptive analysis will consider deaths by cause, as adjudicated by an independent review committee. In addition to the comparisons detailed above, analyses of the whole study period (up to Week 132) will include comparisons of Regimen C with Regimen D. Comparisons of Regimen C and Regimen D using data up to Week 76 were carried out at the time of the primary analysis but considered exploratory.

7.2.3 Proportion of patients experiencing a grade 3 or greater adverse event, as defined by the DAIDS criteria, during treatment and follow-up

The difference in proportion of patients experiencing a grade 3 or greater adverse event, as defined by the DAIDS criteria¹⁰, during treatment and follow-up, between Regimen B and Regimen C, between Regimen B_{mox} and Regimen C, between Regimen B_{lev} and Regimen C, between Regimen B and Regimen D, and between Regimen B and Regimen A, with corresponding two-sided 95% confidence intervals and p-values will be estimated (see Section 6.1.1). The analysis will be stratified by randomisation protocol (as defined in Section 1.6) and HIV status with three strata: HIV negative, HIV positive with CD4 count less than 350 cells/mm³, and HIV positive with CD4 count more than or equal to 350 cells/mm³.

This analysis will be conducted on the whole study period, the study period censored at Week 76, and separately for each phase (Treatment censored at Week 76, and Allocated treatment).

Comparisons will be repeated in subgroups according to HIV infection status. In addition the proportion of participants with cardiac events, hearing loss and hepatotoxicity by Week 76 and Week 132 in Regimen C and Regimen D will be compared to Regimen B.

In addition to the comparisons detailed above, analyses of the whole study period (up to Week 132) will include comparisons of Regimen C with Regimen D. Comparisons of Regimen C and Regimen D using data up to Week 76 were carried out at the time of the primary analysis but considered exploratory.

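### The long-term table of persistent hearing loss (SAP 9.3.3) stops at the last efficacy visit, so it leaves out the scheduled Week 132 hearing test for about a quarter of Regimen B and C patients

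*SAP*

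**What the plan says.** SAP 9.3.3 tabulates, by arm and on the safety population, patients with significant hearing loss. The loss must persist: it has to be "still present at the last visit of the follow-up period being considered (Week 76 or last efficacy visit) and is grade 3 or higher". Only those two periods are named.

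SAP 7.1 ties the efficacy cut-off to the projected Week 96 visit of the last patient randomised, about the end of November 2021. A participant's "scheduled last efficacy visit will be their latest scheduled trial visit on or before this date".

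The rule for safety is different. Protocol 1.1.6 states that with Version 11 "the end of follow-up for efficacy has been brought forward, although follow-up for safety is unchanged". SAP 1.4 agrees: "all data accrued to Week 132 will be used in the long-term safety analysis".

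In Protocol Table 6 the follow-up hearing tests are at "Weeks 52, 76 and 132". The November 2021 cut-off ends routine sputum collection (Protocol 8.1.1) and PK sampling (Table 6, footnote 18). Nothing ends the hearing test.

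Two other SAP sections cover hearing loss. Section 7.2.3 compares Regimens C and D with B on "cardiac events, hearing loss and hepatotoxicity by Week 76 and Week 132", and 9.3.5 tabulates grade 3 or higher events over the whole study period. Section 5.8 governs the grading: "For ECG, laboratory events, weight changes and hearing loss, only the maximum grade within phase will be reported".

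**The concern.** An efficacy cut-off has been applied to a safety outcome, against the SAP's own data rule and without a stated reason. The schedule makes the difference matter. Between Week 76 and Week 132 there is no scheduled hearing test, so a patient whose last efficacy visit falls in that gap gains no scheduled test from the longer period.

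The long-term column would then mix two kinds of result under one label: Week 132 status for most patients, and largely Week 76 status for the rest.

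Regimen C drops the injectable in order to avoid ototoxicity and renal toxicity (Protocol 2.2). Whether hearing loss persists bears directly on that rationale, and 9.3.3 is the only section of this SAP that measures persistence.

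**Working it through.** **Inputs**

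- Share of patients with efficacy outcomes at Week 132 (Protocol 1.1.6): "The majority of patients (approximately 75% on Regimens B and C) will still have efficacy outcomes at Week 132".
- Efficacy follow-up for the others is censored between Weeks 96 and 132, with a stated 3% loss of person-years (Protocol 1.1.6).
- Planned size is 200 per arm, 400 in total (Protocol 11.4.1).
- Visits after Week 84 are every 12 weeks: 96, 108, 120 and 132 (Protocol 8.1.1).
- The cut-off is taken as 30 November 2021.

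**Step 1. Check the 75% against the protocol's own 3%.** The complement is 1 − 0.75 = 0.25. If censoring is uniform over Weeks 96 to 132 (assumption), the mean loss is (132 − 96)/2 = 18 weeks. The person-time lost is 0.25 × 18/132 = 3.4%, which rounds to the stated 3%. The two figures are consistent.

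**Step 2. Patients affected.** 0.25 × 400 = 100, or about 50 per arm if split evenly (assumption). This is before deaths and losses. For the other 75% the last efficacy visit is Week 132, so their test is included.

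**Step 3. Which visit is the last efficacy visit.** Counting back from 30 November 2021: 132 weeks gives 21 May 2019, 120 weeks gives 13 August 2019, 108 weeks gives 5 November 2019, and 96 weeks gives 28 January 2020.

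| Randomised | Last efficacy visit | Hearing test scheduled there? | Weeks since the Week 76 test |
|---|---|---|---|
| 22 May to 13 Aug 2019 | Week 120 | No | 120 − 76 = 44 |
| 14 Aug to 5 Nov 2019 | Week 108 | No | 108 − 76 = 32 |
| 6 Nov 2019 to 28 Jan 2020 | Week 96 | No | 96 − 76 = 20 |

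For all three groups the Week 76 test is 132 − 76 = 56 weeks before the end of safety follow-up.

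**Step 4. Could the visit window rescue the Week 132 test?** SAP 5.3.1 allows at most six weeks (42 days) after the last efficacy visit. From the target days in the SAP visit-window table, the windows end no later than 673 + 42 = 715, 757 + 42 = 799 and 841 + 42 = 883. These are 210, 126 and 42 days before the Week 132 target, day 925. The 12-week COVID-19 extension gives 757, 841 and 925. It reaches day 925 only for a patient whose Week 120 visit was missed because of COVID-19, and it is written for sputum samples.

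**Step 5. Possible effect on the table.** The documents do not say how many patients change status between Weeks 76 and 132. For illustration only, suppose 2%, 5% or 10% of the 50 in one arm change, all in the same direction (assumption). That is 1, 2.5 or 5 patients; divided by 200, the proportion moves by 0.5, 1.25 or 2.5 percentage points.

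**Step 6. Are the data available?** The last Week 132 test falls at 28 January 2020 + 132 weeks = 9 August 2022, before SAP version 6.0 of 9 September 2022.

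**The case against.** The strongest reply is that this is a slip of wording in one non-inferential summary.

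- **The governing rule already covers it.** SAP 1.4 sends all data to Week 132 into the long-term safety analysis, and the first sentence of 9.3.3 speaks of treatment and follow-up without a cut-off. That shows what was probably intended. The parenthesis is still the operative definition, and a programmer who follows it will produce the truncated table.
- **Hearing loss to Week 132 is compared in 7.2.3 and tabulated in 9.3.5.** This stands, and it limits the damage. Those sections report events, with the maximum grade in a phase under 5.8, so resolved and persistent loss count alike. That is a legitimate measure, but a different one.
- **Status may hardly change after Week 76.** Regimen B's injectable is confined to an intensive phase of at most 24 weeks (Protocol 7.3.2), so Week 76 is about 52 weeks later, leaving aside make-up doses and salvage treatment. Protocol 8.3 and 13.2 also call for follow-up of serious or grade 3 or greater events until they resolve or stabilise, so unscheduled tests are plausible for these patients. Both points make a large effect less likely. Neither is a reason to omit a scheduled test.
- **The 25% is a projection, and the Extensive Stage 2 SAP was not available.** Both are true. The 25% is an upper figure for the tests left out, and persistent loss to Week 132 may be reported in that other document.
- **Using the last available test still mixes time points.** It does, but only for patients whose Week 132 test is missing, and the count by arm shows how many they are.

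**Conclusion.** The concern holds. As written, 9.3.3 contradicts the SAP's own safety data rule and leaves out a scheduled hearing test for up to about 25% of Regimen B and C patients: about 100 of 400, on the protocol's projection and the planned sample size. These are patients without a scheduled test in the period, not patients shown to be misclassified.

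The number whose classification would change cannot be derived from the documents, and no bias between arms is shown. The primary analysis and the event-based safety analyses are untouched. The correction should be made because persistent hearing loss is central to the case for an injectable-free regimen and the data are already scheduled.

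**What to change.** In SAP 9.3.3:

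1. Replace the last efficacy visit with Week 132 (end of safety follow-up) as the longer period, and keep the Week 76 version.
2. State that a patient whose Week 132 hearing test is missing is classified on the last available hearing test.
3. Report by arm how many patients have no test after Week 76 and are therefore classified on Week 76 or earlier data.

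Section 7.2.3 needs no change. The trial statisticians are not blinded (Protocol 10.1) and the change would follow SAP version 6.0, so the version history should record it as alignment with the existing rule in SAP 1.4.

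The cost is a few lines of SAP text and one table re-run, including any double programming. No new data collection is needed.
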